### **6.3 Recruitment**

Participants will be recruited from the Village and the community through advertisements, brochures, and flyers (See Appendix A). Targeted locations might include bulletin boards at community grocery stores, physician's offices, medical centers, retirement homes, etc. Occasionally, the project coordinator and investigators will make informational presentations about age-related changes in various community venues (e.g. health fairs, socials). As part of these presentations, we will encourage interested individuals to contact the VITAL lab to learn more ongoing research. Staff members of The Village who obtain signed permission from residents will forward resident names and contact information to the Study Coordinator.

Additional recruitment may occur through the clinics of the PI and co-investigators or other clinics at the Fixel Center (via flyers). These clinics focus on older adults including those with Parkinson disease, and potential participants will be directly asked about their interest in this study by their clinicians. Additionally, flyers will be distributed to other physicians at the Fixel Center.

Finally, recruitment may occur via IRB approved clinical and research databases. Thus, recruitment of normal older adults may take place via two IRB-approved research databases that are maintained by one of the co-investigators, [name]. These include the Claude D. Pepper Recruitment Registry (IRB #201601352, previously 415-2007) and the Participant Registry for Aging Research (IRB #201601448, previously 131-2002).

Recruitment of individuals with mild cognitive impairment or Parkinson disease may take place via INFORM (IRB #201501166, previously #416-2002), a clinical research database that is maintained by the Center for Movement Disorders and Neurorestoration (CMDNR). The INFORM database includes patients with both movement and cognitive disorders, including those who are seen in [name] and [name]'s Cognitive Disorders and Dementia clinics at the Fixel Center.

### **6.4 Inclusion/Exclusion criteria**

#### **6.4a. General Inclusion Criteria for all Participants**

- Age 62 years or above
- Able to provide informed consent and perform cognitive and mood measures on a computer
- Willingness to be randomized to Sham or Real intervention
- Can devote 2 weeks to the intervention, and additional time for pre and post testing
- 8th grade education and ability to read on 8th grade level based on scores on the Wechsler Test of Adult Reading (WTAR) or the Wide Range Achievement Test-IV (WRAT-IV); or a reading test at 14 pt. text
- On stable doses of major medications; Since some older adults with memory complaints may be prescribed acetylcholinesterase inhibitors or related medications by their primary care physicians (i.e., donepezil, rivastigmine, galantamine, memantine, or other potential memory-enhancing agent(s), we will not exclude them as long as they have been on stable medications for at least two months and plan to continue this medication during study participation.

- Willingness to allow a study partner (spouse, family member, friend) to answer questions about their cognitive, mood, and other behaviors. This does not apply to individuals with Parkinson disease.

6.4b. General Exclusion Criteria for All Participants

- Sensory loss (vision, hearing) or motor deficits that would preclude participation in the experimental cognitive tasks or neuropsychological assessment
- Unstable and uncontrolled medical conditions (metabolic encephalopathy, HIV, moderate to severe kidney or liver disease)
- Previous major strokes or other known significant brain abnormalities or diseases affecting cognition (i.e., multiple sclerosis, seizure disorder, brain surgery, moderate TBI, etc.). No history of brain surgery. Exceptions are a diagnosis of Parkinson's disease for the PD subgroup.
- Evidence of potential dementia based on cognitive screening (e.g., scores < 5th %ile on the Montreal Cognitive Assessment (MoCA) or the Dementia Rating Scale-2 (DRS-2) based on appropriate age, education and sex norms.
- Current or past history of major psychiatric disturbance including schizophrenia, or active psychosis, bipolar disorder, current major depressive episode, current alcohol or substance abuse or history thereof within the past six months. This will be assessed using the *Mental Health Screen v.3* (Carroll & McGinley), a modification of the Structured Clinical Interview for DSM-IV psychiatric disorders. We are not excluding individuals who are taking antidepressants or anti-anxiety medications, however, use of antidepressants and anxiolytics will be recorded and data will be analyzed in post-hoc analyses
- Use of antipsychotics, sedatives, or other medications with significant anticholinergic properties (due to potential influence on memory)
- Use of photo-sensitive medications such as steroids or retin-A within 15 days of the study intervention
- Diagnosis of active cancer
- Previous participation in a cognitive training study within the last 6 months

6.4c. Additional criteria for participants in the cognitively normal, MCI, and Parkinson groups:

**Cognitively Normal Group**

- No evidence of objective cognitive decline based on scores on neuropsychological screening measures involving delayed memory (HVLT-R or WMS Story Recall), confrontation naming (Boston Naming Test), and executive function (Trails B, Category Fluency, Judgement of Line Orientation). Scores on these measures must be no lower than -1 standard deviation below normative values.
- Lives independently with no impairment in social or occupational function
- No impairment in social and/or occupational function
- Does not meet DSM-V criterial for Major or Minor Neurocognitive Disorder

**Amnestic MCI Groups – Amnestic and Nonamnestic**

- Subjective memory or cognitive complaints that are confirmed by a study partner
- Global Clinical Dementia Rating (CDR) Scale of 0.5 with CDR sum of boxes no greater than 2.0 (Morris, 1993)

- For amnestic MCI, objective memory impairment based on HVLT-R delayed word list recall or delayed paragraph recall (WMS) of -1.5 standard deviation or below expected levels for age, education, ethnic/culture. Scores on other neuropsychological screening or baseline measures can be no more than 1.5 SD below normative values. Note that an amnestic component is necessary but non-amnestic component is not required.
- For nonamnestic MCI, scores on memory tasks (e.g., delayed recall of stories from WMS) must be within normal limits (e.g., at least -1.0 SD or better than normative values). Scores in the executive domain should be -1.5 SD or below normative values..
- No impairment in social and/or occupational function
- Does not meet DSM-V criteria for Major Neurocognitive Disorder

### **Parkinson Disease Group**

- Participants must have a diagnosis of idiopathic Parkinsons disease by a movement disorders specialist based on UK Brain Bank criteria (Hughes et al., 1992a, 1992b).
- No previous history of brain surgery (DBS, pallidotomy, thalamotomy, or fetal cell implants).
- No evidence of dementia based on scores on a cognitive screener (e.g., Dementia Rating Scale-2 (DRS-2) and score on delayed paragraph recall cannot be lower than 1.0 standard deviation of normative values
- May have difficulties with activities of daily living, but this is due to physical symptoms of Parkinson disease and not because of cognitive problems
- Unwillingness to undergo baseline and followup visits when they are 'off' standard dopamine medication
- Inability to undergo a brain scan

Additional exclusion criteria apply to those individuals who participate in the ***optional brain imaging*** study. The brain scan is optional for all participants except those with Parkinson disease. In that case, inability to undergo a brain scan, before and after intervention, is an exclusion. Exclusion criteria for a brain scan include

- Presence of claustrophobia
- Implants such as pacemakers, heart valves, brain aneurysm clips, orthodontics, non-removable body jewelry, or shrapnel containing ferromagnetic metal.

\*\*Note that we are highly experienced in working with older adults who are identified as experiencing current major depression or other psychological disturbances or who perform below cutoff on standard cognitive screening measures. The PI [[name]] is a boarded clinical neuropsychologist who has been working with this clinical population for over 30 years. The clinical Co-Is ([name], [name], [name], [name]) are experienced neurology clinicians, and the doctoral students on this protocol are clinical psychologists in training with experience in diagnosis and treatment of mood and cognitive disorders. Discussions will be held with individuals of concern and recommendations will be made to appropriate health care providers with permission of the participant and in line with standards of care.

### **6.5 Screening Interview and Measures**

Participants will be screened for inclusion/exclusion criteria. This will involve review of background and demographic information, medical and psychiatric history, current medications, and assessment of functional activities, along with screening of current cognitive

status using the MoCA or DRS-2, the HVLT-R or WMS-III Logical Memory, and other cognitive measures. Screening will be administered by the project coordinator.

**Table 1: Screening & Baseline Measures**

Dementia Screen	Montreal Cognitive Assessment (MoCA: Nasreddine et al., 2005) or Dementia Rating Scale (DRS); these are widely used cognitive screening measures for dementia; See text for cutoff scores for Cognitively Normal and MCI groups
Objective Memory	Hopkins Verbal Learning Test-Revised and the WMS Logical Memory Stories : delayed recall scores on these measures are used to assign participants to Cognitively Normal (CN), amnestic and nonamnestic MCI groups, or to exclude Parkinson patients; (see text)
Other Cognitive measures	Executive Function - Trailmaking Test (Optional: Wisconsin Card Sort) (optional for PD) Visuospatial - Judgement of Line Orientation (JLO) (optional for PD) Language - Boston Naming Test, Category Fluency (optional for PD) Attention & Processing Speed - Digit Span, Digit Symbol (optional for PD)
Medical	Background medical history - rule out medical conditions (i.e., neurodegenerative, TBI, etc.),
	Charlson Comorbidity : Assesses for variety of comorbid medical conditions, computes risk factor score
	List of Medications : stable medications for 3 months; rule out use of anticholinergic medications; rule out use of photo-sensitive medications within 15 days of intervention
Psychiatric	Mental Health Screen V.3 (Carroll & McGinley) - this is modification of Structured Clinical Interview for DSM-IV psychiatric disorders, both current and historical (SCID-IV, First, Spitzer, Gibbon, & Williams); Goal is to rule out major depressive disorder, schizophrenia, psychosis, current substance abuse, and other Axis 1 disorders
Reading Literacy	Wechsler Test of Adult Reading (WTAR) or the reading subtest from the Wide Range Achievement Test –IV (WRAT-IV); participant reads aloud single words in order to estimate reading level; All must read on at least an 8 th grade level
Vision	Vision & Color Vision Screening : Basic visual acuity will be measured using a Snellen chart and color vision will be tested using Ishihara color plates.

Participants will require a **Study Partner** (e.g., spouse, family member, friend) to provide independent information about their cognitive and behavioral status. The study partner will complete structured questionnaires about the participant. Both the participant and the study partner must provide independent consent for this to take place. The requirement for a study partner is 'optional' for those individuals with Parkinson disease.

It is possible that some participants, particularly those in the MCI or Parkinson groups who are recruited through the UF Cognitive Disorders and Dementia clinics or CMNDR, may have already had some of the screening measures, cognitive tasks, and rating scales associated with the current study. If so, we will request permission to use these, rather than repeat them, if they have been completed within 2 months. We will also request permission to access relevant medical and neuroimaging records.

If a participant does not meet inclusion/exclusion criteria, they will be thanked for their participation and given information as to the reason for their screen failure. There are several reasons why a participant might fail inclusion/exclusion criteria. Some that are of particular concern are poor test performance on the dementia screening measures (MoCA or DRS), presence of current major depression, substance abuse, or psychosis (i.e., hallucinations, delusions). If any of these scenarios emerge, we will discuss with the participant and, if appropriate, we will offer a referral for additional clinical evaluation through their primary physician or a specialty health care provider. Should individuals report suicidal ideation, the PI or co-investigators will meet with the participant to assess risk and refer for further evaluation

or treatment if necessary. With participant permission, we will provide results of our screening to their health care provider and/or them or a family member. As mentioned above, the project team is experienced in diagnosis and treatment of mood/cognitive disorders.

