## 6.6 Pre and Post-Intervention Measures

Participants who meet study criteria and who remain interested in participating in the 2 week intervention will be randomized to treatment or sham groups and undergo a baseline/ pre-intervention testing. The pre-intervention measures will be administered by a trained psychometrist or research assistant who will be blinded to group assignment (sham, real NIR stimulation).

The pre-intervention testing will take approximately 3 – 3.5 hours, and will consist of measures of executive function, recent memory, and mood. These same measures will be given after the two-week intervention has completed.

Individuals with Parkinson disease will complete the pre and post intervention visits when they are “off” their typical dopaminergic medications. This is identical to what Parkinson patients are asked to do as part of standard clinical care when seen at the UF Movement Disorders Clinic. To do so, the Parkinson patients will refrain from taking their parkinsonian medications overnight, with no dopa medication after 10:00 PM the night before. The theoretical rationale for evaluating patients when off dopamine medication is to obtain an index of the true status of their disease state.. The remainder of the protocol (i.e., screening, intervention) will be completed when participants are on their normal medications. When tested ‘off medication’, patients may experience increased slowness, tremors and stability. Because of this, they will be closely monitored and provided a wheel chair. If they become too uncomfortable they can take their medication and will be withdrawn from the study.

In previous IRB- approved studies, we have tested Parkinson patients off medication while they completed an array of cognitive, EEG, and other tasks. We have found that the tolerability was quite good and no participants dropped out of the study for the medication issue. In the current study, we are implementing testing ‘off dopa’ medications at the recommendation of the Parkinson Foundation.

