### 6.6.1 Executive Measures [NIH Examiner, Stroop]

The executive measures include the NIH Examiner, a computerized battery consisting of 9 individual subtasks described below, and a measures of cognitive inhibition (Stroop task). During post-intervention, an executive measure given as part of screening (Trail Making Test) will be repeated.

**6.6.1a Description of the NIH Examiner:** The National Institutes of Health Executive abilities: Methods for Neurobehavioral Evaluation and Research (Kramer et al., 2012). The NIH Examiner is a computer based battery that involves nine tasks of frontal-executive function and takes around 45 minutes to complete. Funding for development of the NIH Examiner was provided by NINDS in 2005 to develop sensitive, domain-specific tasks of fronto-executive function. The NIH Examiner consists of 9 individual tasks that can be combined into three domain specific scores: *Cognitive Control, Working Memory, and Fluency*. An overall *Executive Composite* score can also be computed (Kramer et al., 2014). In the current study, the **dependent variable for the primary aim will be the “executive composite”**

score calculated from the tasks within the NIH Examiner. Described below are each of the 9 tasks of the battery.

1. *Dot Counting (working memory)*: Participants look at a mixed array of green circles, blue circles, and blue squares. They are asked to count all of the blue circles and remember the final total, before counting the blue circles on new displays. The number of new displays increases from two to seven over a total of six experimental trials. The dependent variable is total correct score over trials 1-6, which contributes to the Executive Composite and the Working Memory factor scores.

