9. **Unstructured Task** (planning): In this task, participants are presented with three booklets, each containing five pages of puzzles. Puzzles are cognitively simple but may take anywhere from 4 to 60 seconds to complete, and are associated with a specific point value. Participants are given six minutes to complete puzzles and are required to use judgment and planning skills in order to earn as many points as possible. The dependent variable is the total number of points earned during the 6 minutes. The score on this task is not factored in to the Executive Composite or the factor scores.

**6.6.1b. Description of the Stroop** (Golden version). This version of the Stroop is a standard task given as part of the typical neuropsychological exam and is pre-approved by the IRB. It involves 3 parts: Word Reading, Color Naming, and Color-Word Interference. During Word Reading, a participant reads the words (red, blue, green) typed in black ink on a white page, vertically. Final trial score is total number of words read in 45". During Color Naming, the participant rapidly names the color patches (red, green, blue) that are arrayed on a card. Final trial score is total number of patches accurately identified in 45". During the Color-Word Interference condition, a word (i.e., Red) is printed in color ink that differs in meaning from the meaning of the written word. The participant's task is to name the ink color of the word, and inhibit reading the word. Final trial score is total number of items identified over 45". The **dependent variable** is the cognitive inhibition score, which is based on the Color-Word interference score, taking into account performance on the 2 baseline trials.

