### **6.6.2 Recent Memory Tasks** [AVLT, Arena Task, MST]

The recent memory measures include a verbal word list learning task (AVLT), a spatial navigation and learning measure (ARENA), and an object recognition memory task (MST). During post-intervention, the memory measure given as part of screening (Logical Memory Stories) will be repeated.

**6.6.2a. Description of the Auditory Verbal Learning Test (AVLT):** The AVLT is a word list learning task that assesses learning, proactive interference, along with retention and recognition over 30 minute delays (Rey, 1964; Schmidt, 1996). It is widely used in clinical settings and is similar to other word list learning tasks, except that the individual items are not semantically related to each other. Thus, participants must impose their own unique strategies in order to optimize learning. The AVLT consists of two 15 item lists, with List A given over 5 trials, followed by one presentation of List B, with subsequent immediate recall of List B, then List A. Later 30 minute recall and recognition of List A are obtained. The primary dependent variables for this task are overall learning, the degree of proactive interference, and delayed recall after 30 minutes.

**6.6.2b. Description of Computerized Arena Task** (Laurance et al., 2012): This is a task of spatial memory and navigation that has been linked to hippocampal function and is a human analogue to the Morris water maze used in animal studies. At UF, this task has been used in other IRB-approved studies with older adults (the VITAL study), those with Essential tremor, those with mild cognitive impairment and Alzheimer's disease.

[figure not shown]
The task is given on a computer and participants are trained in the use of a joystick or direction pad before beginning the task. Participants must navigate in a virtual, 3-D room displayed on a computer screen. They must start from different positions to find an invisible target on the

floor as quickly and efficiently as possible. Shown below are sample walls of the virtual room. The overall goal is to find a 'hidden target' on the floor of the arena.

[figure not shown]
The participant uses either a direction pad or joystick to navigate this "arena".

Navigation is constrained to a circular "arena" designed to look like a pool of water (the blue on the pictures above). The arena is bordered by a low wall and is in its entirety located in a perfectly square room, with each of the four

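### Clinic results up to two months old may stand in for study testing, and the protocol does not exempt measures that are analysed pre-post

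*Protocol*

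**What the plan says.** Protocol section 6.5, in the text after Table 1, expects that certain recruits, chiefly MCI and Parkinson patients who come from the university's own clinics, "may have already had some of the screening measures, cognitive tasks, and rating scales associated with the current study". It continues: "we will request permission to use these, rather than repeat them, if they have been completed within 2 months". The only conditions are permission and the two-month limit. Nothing is said about who gave the test, whether the person was on or off medication, or whether the measure is later analysed as an outcome.

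Section 6.6 describes the pre-intervention battery differently: "The pre-intervention measures will be administered by a trained psychometrist or research assistant who will be blinded to group assignment". It adds: "These same measures will be given after the two-week intervention has completed". Parkinson participants are to be off dopaminergic medication at the pre and post visits and on their usual medication at screening.

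Two tests belong to both screening and follow-up. Section 6.6.1 says that at post-intervention "an executive measure given as part of screening (Trail Making Test) will be repeated", and section 6.6.2 says that "the memory measure given as part of screening (Logical Memory Stories) will be repeated". Table 2 marks HVLT-R/Logical Memory at Screening and Follow-up with no Baseline mark. It marks Trail Making at Baseline and Follow-up.

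**The concern.** The rule lists cognitive tasks and rating scales separately from screening measures, so on its face it reaches beyond eligibility. Followed as written, the pre value of an outcome may be a clinic score from another tester, taken weeks before the study baseline. That does not fit the tester and the pre-post sequence set out in section 6.6.

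Section 7.3 analyses each cohort separately by group and occasion, with change scores as a further technique. Both rest on the pre score. If some pre scores in a cohort come from the clinic and others from the study visit, participants' changes span different intervals, testers and possibly medication states. The cohorts named are also the small ones. This is a rule about data collection, so an analysis plan cannot repair it once the baseline test has been skipped.

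**Working it through.** No figure in the protocol is at stake, so there is none to reproduce. The check is of the text, followed by an illustration of size.

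**1. Does the text exempt outcomes?** Section 6.5 covers screening measures, cognitive tasks and rating scales. Section 6.6, section 9 and Table 2 provide for baseline testing, but none says that it must take place whatever clinic results exist. No exemption is stated.

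**2. Does a screening-only reading remove the problem?** No. Sections 6.6.1 and 6.6.2 describe Trail Making and Logical Memory as screening tests that are repeated after the intervention. Since Table 2 gives Logical Memory no Baseline mark, a reused clinic result would be its only pre score.

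**3. Which outcomes are exposed?**

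- Stroop: section 6.6.1 says "This version of the Stroop is a standard task given as part of the typical neuropsychological exam". Section 7.1 lists its interference score under the co-primary executive outcome.
- AVLT: section 6.6.2 describes it as in wide clinical use. Section 7.1 lists its delayed recall under the co-primary memory outcomes.
- BDI-II, STAI, Apathy Scale and POMS (Aim 2 secondary) and UPDRS (Aim 4): all are pre-post outcomes in section 7.1.
- NIH Examiner, Arena and NIH Toolbox: these are computerised batteries that the protocol does not describe as clinic tests, so they are unlikely to be affected.

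**4. How many people?** From section 6.2, the named groups are 20 + 20 + 40 = 80 of 70 + 80 = 150 planned, or 53%. There are 10 per arm in each MCI group and 20 per arm in Parkinson disease. Only those with a recent result on the same measure are affected.

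**5. Interval.** The intervention lasts 14 days. A result up to about 61 days older gives 14 + 61 = 75 days, and 75/7 = 10.7 weeks. This counts the two months back from the first stimulation session and puts the post-test straight after the last. The protocol fixes neither point.

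**6. Precision (illustration).** With two occasions, the group-by-occasion test is a comparison of mean change. With equal pre and post SDs, set to 1, the variance of change is 2(1 − ρ). If a share p of pre scores is reused, and mean change is the same for reused and study scores:

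variance = (1 − p) × 2(1 − ρ_study) + p × 2(1 − ρ_reused)

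With ρ_study = 0.8 and ρ_reused = 0.6, the two components are 0.40 and 0.80:

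- p = 25%: variance 0.50, ratio 0.50/0.40 = 1.25, standard error × √1.25 = 1.118
- p = 50%: variance 0.60, ratio 1.50, standard error × 1.225
- p = 100%: variance 0.80, ratio 2.00, standard error × 1.414

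The protocol gives neither correlation, so the range matters:

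| ρ_study → ρ_reused | 25% reused | 50% reused | 100% reused |
|---|---|---|---|
| 0.8 → 0.7 | +6% | +12% | +22% |
| 0.8 → 0.6 | +12% | +22% | +41% |
| 0.8 → 0.5 | +17% | +32% | +58% |

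The 100% column is an outer bound, because section 6.5 speaks of some participants and some measures.

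In terms of detectable difference, assuming two-sided 5% and 80% power (the protocol states neither), the formula is (1.960 + 0.842) × √(2/n) × SD of change. For 0.8 → 0.6:

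| Per arm | No reuse | 25% | 50% | 100% |
|---|---|---|---|---|
| 20 | 0.56 SD | 0.63 SD | 0.69 SD | 0.79 SD |
| 10 | 0.79 SD | 0.89 SD | 0.97 SD | 1.12 SD |

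**The case against.** The best reply is context. The sentence sits in the screening section, while outcome collection has its own section, its own visit of 3 to 3.5 hours and its own column in Table 2. No outcome section mentions clinic scores. One can read the specific baseline rules as governing outcomes. That makes it a matter of what could happen, not what would. It does not remove the conflict, because the wording is broader than screening and two screening tests are themselves repeated after treatment.

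A reader might infer three stronger things that the documents do not support.

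- **That the comparison of arms is biased.** Reuse is decided at screening, before randomisation under section 6.6, and a score obtained then cannot depend on arm. What remains is noise, and chance imbalance in small arms.
- **That the main endpoints are compromised.** The dependent variables named in sections 6.6.1, 6.6.2 and 6.6.4 are the Examiner composite, the Arena composite and the Toolbox scores. Clinic records are unlikely to hold these. The co-primary exposure is through Stroop and AVLT.
- **That a reused UPDRS would be on medication.** Sections 6.6 and 12 describe routine movement-clinic visits as off medication. The open question is other clinic testing, for which no state is given.

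The practice argument also cuts both ways. With reuse, a clinic recruit meets a test twice, as a community recruit does. Retesting at baseline makes it three times. This stands as a cost of the fix. Lastly, this is a pilot meant to estimate effect sizes and feasibility, which limits the consequence, although noisy change scores bear directly on an effect-size estimate.

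**Conclusion.** The point holds as an unreconciled conflict between sections 6.5 and 6.6. Some pre scores on Stroop, AVLT, Trail Making, Logical Memory, mood scales or UPDRS could come from another tester, up to about 10 to 11 weeks before the post score, with medication state unspecified. This would add noise and make change scores non-comparable within cohorts of 10 to 20 per arm. It would not systematically favour either arm.

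The size cannot be fixed from the protocol, because it depends on the share reused and on correlations that are not given. A fall from 0.8 to 0.6 would raise the standard error about 12% at 25% reuse and 22% at 50%. If reuse did not lower the correlation, this loss would be nil. If mean change also differed between reused and study scores, the spread within each arm would be larger than shown.

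**What to change.** In section 6.5, limit reuse to tests that serve eligibility only. Add that every measure analysed pre-post is given by study staff before the intervention, at the visit where Table 2 places it: the study screening visit for HVLT-R/Logical Memory, and the baseline visit for the others. Requiring everything at the baseline visit would add a further Logical Memory administration for all participants.

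Reconcile sections 6.5 and 6.6 on medication state for Parkinson participants. This includes Logical Memory, whose study pre score is taken at screening (on medication) and whose post score is taken at follow-up (off medication).

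The cost is some participant time, largely at visits already planned, and one additional practice exposure for clinic recruits who had the same test recently. Recording the date of any clinic test within the two months would let that exposure be described.
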